9.3.1.2 Futility Monitoring

For trial monitoring, “success” will be defined separately by tumor group. For participants with CD8 low tumors, participants will be counted as having success if they meet the definition of CBR *or* if the tumor converts from CD8 low to CD8 high expression. For participants in the CD8 high tumor group, participants will be counted as success if they meet the definition of CBR. Denote the probability of success by θ_s . We assume $\theta_s \sim \text{beta}(0.4, 1.6)$. The stopping rule is given by the following probability statement: $\Pr(\theta_s < 0.20 \mid \text{data}) > 0.975$. That is, participant enrollment for advanced metastatic cancer arms will be stopped if, at any analysis time, it is determined that there is > 97.5% chance that the CBR is < 20%, a constant rate that is at the average expected response rate for these participants. The stopping boundaries for this futility

rule, shown in [Table 14](#), are designed to terminate enrollment on the arm if the number of overall responses compared with the number of participants enrolled who are evaluable does not meet the requirements of this table. A participant is evaluable for benefit either on the date of disease assessment or the date the participant goes off study without benefit or if the participant does not receive the scheduled disease assessment within 3 weeks without associated scheduling delay. Monitoring will be carried out during enrollment in each advanced metastatic cancer arm. Participants who withdraw from the study after receiving treatment but before undergoing on-treatment biopsies or who miss the evaluation window without associated treatment delay will be counted as not benefitting and therefore evaluable for analysis. CBR is defined as best response of CR or partial response (PR) any time or stable disease (SD) lasting 6 months. For futility monitoring purposes, confirmation of response (CR or PR) is not required. Additionally, a participant who has been on study between 12 weeks and 6 months and has SD at the time of data collection will be counted as a success for that futility analysis. If that participant later progresses and no longer meets the SD definition, their updated information will be included in the monitoring analysis ([Table 14](#)).

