9.3.1.3 Joint Operating Characteristics for Safety and Futility Monitoring

The rules above will apply independently to each CD8 high or CD8 advanced metastatic cancer arm. It is estimated that there will be 40 participants with CD8 high tumors and 160 participants with CD8 low tumors in presenting the operating characteristics below. The probability of stopping at 20 participants provides the probability of stopping early in the CD8 high tumor group, assuming only 40 participants are entered. [Table 15](#) shows the operating characteristics under varying toxicity and response rates.

Table 15: Operating Characteristics Under Varying Toxicity and Response Rates

True Overall Toxicity Rate	True Overall Response Rate	Probability of Stopping at 20 Participants	Probability of Stopping Before 160 Participants	Median (25 th %ile, 75 th %ile) for “Cold” Cohort
0.10	0.05	0.74	>0.99	20 (20, 40)
	0.10	0.39	0.96	40 (20, 80)
	0.20	0.07	0.12	160 (160, 160)
	0.30	0.01	0.01	160 (160, 160)
	0.40	0.001	0.001	160 (160, 160)
0.20	0.05	0.74	>0.99	20 (20, 40)
	0.10	0.39	0.96	40 (20, 80)
	0.20	0.07	0.12	160 (160, 160)
	0.30	0.01	0.01	160 (160, 160)

True Overall Toxicity Rate	True Overall Response Rate	Probability of Stopping at 20 Participants	Probability of Stopping Before 160 Participants	Median (25 th %ile, 75 th %ile) for “Cold” Cohort
	0.40	0.001	0.001	160 (160, 160)
0.30	0.05	0.74	>0.99	20 (20, 40)
	0.10	0.39	0.96	40 (20, 80)
	0.20	0.07	0.12	160 (160, 160)
	0.30	0.01	0.01	160 (160, 160)
	0.40	0.002	0.002	160 (160, 160)
0.40	0.05	0.74	>0.99	20 (20, 40)
	0.10	0.40	0.96	40 (20, 80)
	0.20	0.09	0.19	160 (160, 160)
	0.30	0.03	0.09	160 (160, 160)
	0.40	0.02	0.08	160 (160, 160)
0.50	0.05	0.77	>0.99	20 (20, 20)
	0.10	0.47	0.99	40 (20, 60)
	0.20	0.19	0.78	80 (40, 140)
	0.30	0.14	0.75	80 (40, 140)
	0.40	0.13	0.75	80 (40, 160)

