#### 5.4.1 Primary Efficacy Endpoints

The co-primary endpoint of CBR will be reported among all participants within each study intervention group with a 95% credible interval assuming a beta (0.4, 1.6) prior. CBR is the proportion of participants who show clinical benefit, defined as CR, PR, or SD for  $\geq 6$  months as best response by RECIST v1.1 (Eisenhauer, 2009). Per RECIST, to be assigned a best overall response of complete response (CR) or partial response (PR), changes in tumor measurements must be confirmed by a repeat assessment that should be performed no less than 4 weeks after the criteria for response are first met. The duration of SD is defined as the time from the date of first dose of study intervention until the date of radiographic disease progression per RECIST. If no radiographic progression has occurred and the most recent tumor assessment with overall response of SD occurred  $< 6$  months after the date of first dose of study intervention, the participant will not have met the SD duration criterion and will not

be considered a CBR responder. Participants who do not have a disease assessment will be counted as not having clinical benefit.

For the second co-primary endpoint, the absolute change in the percentage of CD8 cells in on-treatment biopsies from baseline will be reported with a 95% credible interval with no prior for participants in the on-treatment biopsy population. In addition, the number of participants with baseline percentage of CD8 counts < 15% who “convert” from a cold to hot tumor (any on-treatment biopsy with percentage of CD8 counts  $\geq$  15%) will be summarized. The proportion of participants who convert from cold to hot will be reported with a 95% credible interval with no prior.

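### Futility looks credit stable disease from 12 weeks against a benchmark for 6-month clinical benefit, so Table 15 gives stopping probabilities by interim success rate, not by true CBR

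*Protocol*

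**What the plan says.** Protocol 9.3.1.2 stops enrolment to an arm on this condition: "it is determined that there is > 97.5% chance that the CBR is < 20%, a constant rate that is at the average expected response". The endpoint is defined in the same section: "CBR is defined as best response of CR or partial response (PR) any time or stable disease (SD) lasting 6 months". In the CD8-high group, success is CBR alone; in the CD8-low group, CD8 conversion also counts.

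For the looks themselves, three further rules apply:
- SD before 6 months: a participant "on study between 12 weeks and 6 months and has SD at the time of data collection will be counted as a success".
- Response: "For futility monitoring purposes, confirmation of response (CR or PR) is not required".
- Correction: "If that participant later progresses and no longer meets the SD definition, their updated information will be included in the monitoring analysis".

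The final analysis is stricter. Under SAP 5.4.1, if there is no progression but the last SD assessment falls short of 6 months, "the participant will not have met the SD duration criterion and will not" count as a CBR responder.

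On timing, "A participant is evaluable for benefit either on the date of disease assessment" or on going off study without benefit. The Schedule of Activities for the metastatic arms puts the first scan at Cycle 4 Day 1.

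Table 14 stops an arm at 20 evaluable participants if there is at most 1 success. Table 15 is indexed by a true overall response rate. Where toxicity is low it gives 0.74, 0.39 and 0.07 as the probability of stopping at 20, for rates of 5%, 10% and 20%. Section 9.3.1.3 adds: "The probability of stopping at 20 participants provides the probability of stopping early in the CD8 high tumor group", on the assumption that 40 participants enter that arm.

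**The concern.** The look counts an easier event than the one the 20% benchmark describes. Call SD that is present at 12 weeks but progresses before 6 months transient SD. Such a participant is a success at a look inside that window and a failure in the final analysis. The success rate at the look therefore exceeds the true CBR whenever transient SD occurs, and the arm is less likely to stop than a table read by true CBR would suggest.

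This matters most for the CD8-high arm. Its success definition has no conversion component, and the only early-stopping probability the protocol gives for it is the column at 20. The synopsis says there is no independent monitoring committee, so the written rule and its stated operating characteristics carry the safeguard.

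**Working it through.** **1. Reproduce the plan's figures.** Inputs: prior beta(0.4, 1.6), benchmark 0.20, cut-off 0.975 (Protocol 9.3.1.2).
- With 1 success in 20 the posterior is beta(1.4, 20.6), and P(rate < 0.20) = 0.978, above 0.975: stop.
- With 2 in 20 it is 0.904: continue. The limit is 1, as in Table 14.

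P(stop at 20) = P(X ≤ 1) = (1−p)^20 + 20p(1−p)^19:
- p = 0.05: 0.358 + 0.377 = 0.736 (Table 15: 0.74)
- p = 0.10: 0.122 + 0.270 = 0.392 (0.39)
- p = 0.20: 0.012 + 0.058 = 0.069 (0.07)

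All 14 limits in Table 14, and the 20 rows of Table 15 that were checked, reproduce with one fixed success probability per participant. Table 15 therefore makes no allowance for provisional SD.

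**2. Effect of provisional success, exact.** Let d be the share of participants counted at the look only through provisional SD. The rate at the look is p = CBR + d, put into the same formula:

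| d (points) | true CBR 10% | true CBR 5% |
|---|---|---|
| 0 | 0.39 | 0.74 |
| 2 | 0.29 | 0.59 |
| 5 | 0.18 | 0.39 |
| 10 | 0.07 | 0.18 |

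**3. A plausible size for d.** The documents give neither the transient-SD share nor an accrual rate. Assumptions:
- Transient SD in 10-30% of participants, progressing uniformly between weeks 12 and 26.
- CD8-high accrual of 0.2-0.4 per week. Forty participants then take 40/0.2 = 200 to 40/0.4 = 100 weeks, against a study of about 4 years (Protocol 4.5).
- The look takes place when the 20th participant reaches week 12. Anyone who has already progressed is not credited.

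Simulated P(stop at 20) at 0.2 / 0.3 / 0.4 per week:

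| transient SD | true CBR 10% | true CBR 5% |
|---|---|---|
| 10% | 0.34 / 0.32 / 0.30 | 0.66 / 0.64 / 0.61 |
| 20% | 0.29 / 0.26 / 0.23 | 0.60 / 0.54 / 0.49 |
| 30% | 0.24 / 0.20 / 0.17 | 0.52 / 0.45 / 0.38 |

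**4. Evaluability clock.** Three 3-week cycles put the first scan at about week 9, while the SD credit starts at week 12. The protocol does not say which assessment makes a participant evaluable, nor how SD at weeks 9-12 is scored. Suppose it were scored as not yet a success, and half of CBR were SD (assumed). Stopping at CBR 10% with no transient SD would rise from 0.39 to about 0.41-0.42. With 10-20% transient SD it would still be 0.27-0.36. Allowing for such timing conventions, the overall ranges are roughly 0.16-0.38 (CBR 10%) and 0.36-0.70 (CBR 5%).

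**5. Effect of re-classification at later looks.**
- CD8-low, assumed 0.8-1.6 per week, conversion ignored: at CBR 10% the first-look value falls from 0.39 to 0.24-0.01, but stopping before 160 falls only from 0.96 to 0.94-0.77. At CBR 5% it stays above 0.99.
- CD8-high, if the limit of 1 is re-applied at every count from 20 to 39: the cumulative probability is about 0.30-0.39 (CBR 10%) and 0.65-0.72 (CBR 5%). Without transient SD re-application adds nothing, since at most 1 success at a later count implies at most 1 at 20.

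Unconfirmed CR/PR pushes in the same direction as provisional SD; it was not sized.

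**The case against.** The strongest reply is that this is an open and lenient choice. The credit and its later correction are both written down. Giving ongoing SD the benefit of the doubt avoids stopping an arm too early. The study is exploratory and not powered for testing (SAP 5.4), and the final CBR still requires 6 months. All of that stands, and it is why the credit itself need not go. It does not make Table 15 a description of the rule by true CBR.

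A second reply is that the CD8-high limit is not confined to one look. Table 14 applies at the listed number or more, and monitoring is ongoing during enrolment. This has force: step 5 shows that most of the loss is recovered if the limit is re-applied. But the protocol does not say that it will be, and 9.3.1.3 presents only the look at 20.

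A reader might go further and infer any of the following, which the documents do not support:
- That Table 15 is miscalculated. It reproduces; the fault lies in what its rate is taken to mean.
- That the 12-week credit switches the CD8-high safeguard off, with stopping near 0.02 at CBR 10%. That follows from adding the whole transient-SD share in the window to CBR, which credits people who have already progressed, and from 20 CD8-high participants in 6 months. With 40 of 200 expected to be CD8 high, that pace means about 20 × 200/40 = 100 participants overall in 6 months, which fits poorly with a study of about 4 years.
- That a missed stop at 20 cannot be recovered. The wording of Table 14 leaves room for it.
- That SD at weeks 9-12 is scored as failure. No section says so.

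**Conclusion.** The point holds as a mismatch between a stated operating characteristic and the rule it describes. The n=20 values in Table 15 are right for the success rate counted at the look and are not stopping probabilities by true CBR. Under the assumptions in step 3 and the timing conventions in step 4, the CD8-high chance of stopping at 20 is roughly 0.16-0.38 instead of 0.39 at a true CBR of 10%, and 0.36-0.70 instead of 0.74 at 5%. The direction is certain if any transient SD is in the window at the look, apart from the small opposite effect of the week-9 clock. The size rests on assumed transient-SD and accrual rates; with no transient SD the table holds. The CD8-low column for stopping before 160 is largely protected by re-classification. The final CBR analysis is unaffected.

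**What to change.** Keep the 12-week credit and make three changes in Protocol 9.3.1.2 and 9.3.1.3:
1. Relabel the rate in Table 15, and the sentence on CBR being below 20%, as the interim success rate. Restate the stopping probabilities by true CBR over an assumed range of transient-SD rates and accrual.
2. State when the CD8-high limit is applied between 20 and 40 evaluable participants.
3. Start evaluability at one fixed time for all participants, matched to the start of the SD credit.

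Do not instead hold SD back as undecided while counting progression at once. Failures would then enter the denominator from about week 9 and SD successes only at month 6, so the first 20 evaluable would over-represent failures. At a true CBR of 20%, with assumed 20% transient SD and half or a quarter of CBR being CR/PR, the chance of stopping at 20 rises from 0.07 to about 0.09-0.11 at 0.2-0.4 per week, and to about 0.17 at 0.8 per week.

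The cost is a wording change and a rerun of the operating characteristics. The stated stopping probabilities will look somewhat less favourable.

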9.3.1.3 Joint Operating Characteristics for Safety and Futility Monitoring

The rules above will apply independently to each CD8 high or CD8 advanced metastatic cancer arm. It is estimated that there will be 40 participants with CD8 high tumors and 160 participants with CD8 low tumors in presenting the operating characteristics below. The probability of stopping at 20 participants provides the probability of stopping early in the CD8 high tumor group, assuming only 40 participants are entered. [Table 15](#) shows the operating characteristics under varying toxicity and response rates.

Table 15: Operating Characteristics Under Varying Toxicity and Response Rates

True Overall Toxicity Rate	True Overall Response Rate	Probability of Stopping at 20 Participants	Probability of Stopping Before 160 Participants	Median (25 th %ile, 75 th %ile) for “Cold” Cohort
0.10	0.05	0.74	>0.99	20 (20, 40)
	0.10	0.39	0.96	40 (20, 80)
	0.20	0.07	0.12	160 (160, 160)
	0.30	0.01	0.01	160 (160, 160)
	0.40	0.001	0.001	160 (160, 160)
0.20	0.05	0.74	>0.99	20 (20, 40)
	0.10	0.39	0.96	40 (20, 80)
	0.20	0.07	0.12	160 (160, 160)
	0.30	0.01	0.01	160 (160, 160)

True Overall Toxicity Rate	True Overall Response Rate	Probability of Stopping at 20 Participants	Probability of Stopping Before 160 Participants	Median (25 th %ile, 75 th %ile) for “Cold” Cohort
	0.40	0.001	0.001	160 (160, 160)
0.30	0.05	0.74	>0.99	20 (20, 40)
	0.10	0.39	0.96	40 (20, 80)
	0.20	0.07	0.12	160 (160, 160)
	0.30	0.01	0.01	160 (160, 160)
	0.40	0.002	0.002	160 (160, 160)
0.40	0.05	0.74	>0.99	20 (20, 40)
	0.10	0.40	0.96	40 (20, 80)
	0.20	0.09	0.19	160 (160, 160)
	0.30	0.03	0.09	160 (160, 160)
	0.40	0.02	0.08	160 (160, 160)
0.50	0.05	0.77	>0.99	20 (20, 20)
	0.10	0.47	0.99	40 (20, 60)
	0.20	0.19	0.78	80 (40, 140)
	0.30	0.14	0.75	80 (40, 140)
	0.40	0.13	0.75	80 (40, 160)

9.4 STATISTICAL ANALYSES

The study will use an adaptive approach, with on-treatment data guiding trial adaptation and success or futility of each combination in each study subpopulation.

The statistical analysis plan will be developed and finalized before database lock and will describe the study populations to be included in the analyses and procedures for accounting for missing, unused, and spurious data. The statistical analysis plan will serve as a complement to the protocol and supersedes it in case of differences. This section is a summary of the planned statistical analyses of the primary and secondary endpoints.

9.4.1 Efficacy Analyses

The efficacy analysis will be based on the modified Intent-to-Treat (mITT) Population, which comprises all enrolled participants with sufficient biopsy results to be assigned to a treatment arm and who received at least one dose of study drug, unless otherwise specified. Participants will be analyzed according to the study intervention to which they were assigned.

The primary endpoint of CBR will be reported among all participants within each study intervention group with a 95% credible interval assuming a beta (0.4, 1.6) prior. Per RECIST, to

be assigned a best overall response of CR or PR, changes in tumor measurements must be confirmed by a repeat assessment that should be performed no less than 4 weeks after the criteria for response are first met. Participants who do not have a disease assessment will be counted as not having clinical benefit. In addition, CBR and similar credible intervals will be reported for each tumor site and study intervention subgroup that has at least 10 participants.

The proportion of participants whose tumors change from CD8 low to CD8 high expression will be reported with a 95% credible interval with no prior as this is the first look.

For secondary endpoints, baseline CD8 counts will be explored for association with CBR using logistic regression models and with OS using Cox regression models. Multivariate models will be explored with up to 1 variable for every 10 events. For CBR prediction, an event is an objective response (CR or PR or SD as defined above). For association with survival, an event is a participant death.

Among the On-treatment Biopsy Population, both the baseline and on-treatment biopsies will be associated with response and survival using similar logistic and Cox regression models described above, assuming there are sufficient events to carry out the regression analyses. The association of CD8 changes from baseline to on treatment with clinical outcomes will also be explored.

The exploratory endpoint of changes in PSA (absolute and percent) from baseline will be analyzed by cohort for advanced prostate cancer participants.

9.4.2 Safety Analyses

The safety analysis will be based on the Safety Population, which comprises all participants who receive at least one dose of study drug. Participants will be analyzed according to the study intervention actually received.

Safety and tolerability will be assessed through AEs, clinical laboratory parameters, vital signs, and ECGs.

AEs will be described by grade and attribution for each study intervention.

9.4.3 Other Analyses

Biomarker exploratory analyses will be performed when possible and included in the clinical study report or a separate research report.

9.4.3.1 Biomarker Analysis

Descriptive statistics will be used to evaluate the exploratory biomarkers. Biomarker analysis will be further described in a biomarker analysis plan.

9.4.3.2 Patient-Reported Outcomes Analysis

An exploratory analysis may be performed with the patient-reported dataset collected via ApricityCare™, including but not limited to the frequency with which participants complete the daily symptom survey in ApricityCare™, and the frequency of Apricity website access by investigative sites.

10 SUPPORTING DOCUMENTATION AND OPERATIONAL CONSIDERATIONS

10.1 APPENDIX 1: REGULATORY, ETHICAL AND STUDY OVERSIGHT CONSIDERATIONS

10.1.1 Compliance with Laws and Regulations

This study will be conducted in full conformance with the International Council for Harmonisation (ICH) E6 guideline for Good Clinical Practice (GCP) and the consensus ethical principles derived from international guidelines, including the Declaration of Helsinki and Council for International Organizations of Medical Sciences International Ethical Guidelines, and applicable laws and regulations. The study will comply with the requirements of the ICH E2A guideline (Clinical Safety Data Management: Definitions and Standards for Expedited Reporting). Studies conducted in the United States or under a U.S. Investigational New Drug (IND) application will comply with U.S. FDA regulations and applicable local, state, and federal laws. Studies conducted in the European Union or European Economic Area will comply with the E.U. Clinical Trial Directive (2001/20/EC).

10.1.2 Institutional Review Board or Independent Ethics Committee

The protocol, protocol amendments, ICF(s), Investigator's Brochure, any information to be given to the participant, and relevant supporting information must be submitted to the IRB/IEC and reviewed and approved by the IRB/IEC before the study is initiated. In addition, any participant recruitment materials (eg, advertisements) must be approved by the IRB/IEC.

Any amendments to the protocol will require IRB/IEC approval before implementation of changes made to the study design, except for changes necessary to eliminate an immediate hazard to study participants or changes that involve logistical or administrative aspects only (eg, change in Medical Monitor or contact information).

The Investigator will be responsible for the following:

- Providing written summaries of the status of the study to the IRB/IEC annually or more frequently in accordance with the requirements, policies, and procedures established by the IRB/IEC
- Notifying the IRB/IEC of SAEs or other significant safety findings as required by IRB/IEC procedures
- Promptly documenting and reporting any deviations that might have an impact on participant safety and data integrity to the Sponsor and to the IRB/IEC in accordance with established requirements, policies and procedures

- Providing oversight of the conduct of the study at the site and adherence to requirements of 21 CFR, ICH guidelines, the IRB/IEC, European regulation 536/2014 for clinical studies (if applicable), and all other applicable local regulations.

The IRB of Record is MD Anderson and the Relying IRBs are UCLA, UCSF, Stanford, DFCI, and MSKCC. Parker maintains separate documentation of the institution's address, FWA number and expiration date, and the named Institutional Official and IRB Contact, as well as their email and phone numbers and will provide that to the sites.

10.1.3 Financial Disclosure

Investigators and Subinvestigators will provide the Sponsor with sufficient, accurate financial information as requested to allow the Sponsor to submit complete and accurate financial certification or disclosure statements to the appropriate health authorities. Investigators are responsible for providing information on financial interests during the course of the study and for 1 year after completion of the study (see definition of end of study in [Section 4.5](#)).

